4.1.3 DESCRIPTION OF TREATMENTS

After an administration of two oral doses in the first day of treatment (one dose in the morning and one dose in the evening, each dose administered with 2 capsules containing 60 mg of the active substance or placebo), a single daily oral dose of raloxifene (60 mg Group 1, 120 mg Group 2 – treatment groups) or placebo (Group 3 - control group) will be taken on by the patients for two weeks.

The patients will be randomly (1:1:1) assigned to receive either raloxifene treatment or placebo:

- Treatment groups:
 - Group 1: will receive one capsule of raloxifene 60 mg and one capsule of placebo.

- Group 2: will receive two capsules of raloxifene 60 mg.
- Control group:
 - Group 3: will receive two capsules of placebo.

4.1.4 DESCRIPTION OF THE STUDY FLOW

This study will be performed in clinical centers located in Europe. At each study center, the Principal Investigator (PI) will be responsible for ensuring that the investigation is conducted according to the signed Investigator agreement, the protocol, GCP guidelines, and local regulations.

Screening investigations on patient will be done only after signing of informed consent.

At the end of the screening period, patients meeting the entry criteria for this study will be randomized (1:1:1) to 1 of 3 treatment groups (group 1, group 2 or group 3) and instructed by a physician on the correct self-administration of the treatment and completion of the patient diaries.

The study will be a total of 5 weeks in duration:

Screening Period	10 days
Treatment Period	2 weeks (14 days)
Follow-up Period	2 weeks (14 days)

A quality of life questionnaire will be submitted at 3 months after the randomization.

4.1.5 SCHEDULE OF ASSESSMENTS

Assessment of efficacy and safety will be done periodically during the study as given in the schedule of assessment table in protocol section 2.

4.2 PLANNED ANALYSES

Statistical analysis and reporting will be performed by Agati Clinical Informatics, India for this study.

SAS source (raw) data will be transferred as SAS dataset (.sas7bdat), together with laboratory reference range, and any support datasets. Transfer will occur via secured EXOM Group Share Point Portal with limited and restricted access.

The statistical analysis will be based on validated analysis datasets prepared by Agati Clinical Informatics, India.

Production SAS programmers will create derived datasets from the Source (Raw) datasets as per the mapping instructions given in the analysis mapping specifications. Simultaneously, the Validation (QC) SAS programmer will create the same derived datasets independently and will do a comparison with production datasets to validate them.

Validated draft derived datasets will be sent to the Study Lead Biostatistician for review and approval. When the final source data transfer is made available (after database lock), the production and validation programs will be re-run to create the final derived datasets deliverable to be used for the final statistical analysis.

The statistical SAS output generated after running SAS programs will be copied in a Word file and paginated as specified in the Section 18 of this SAP.

Tables, Listings and Figures will be presented according to TFL Shells document created and finalized based on approved version of the SAP.

4.3 INTERIM ANALYSIS

An interim analysis was planned for this study when half (i.e 50 participants per arm (N=150)) of the planned evaluable patients would have reached the primary endpoints at 7 and 14 days (i.e., assessments available).

The intent of the interim analysis was either for identification of early superiority of raloxifene (early efficacy), or for an early stop of one or both treatment arms for futility, or for blind sample size reassessment.

Due to the premature interruption of the enrolment (with 68 patients included in the study), no interim analysis will be done.

4.4 OVERALL ANALYSIS

Final analyses identified in this SAP will be performed by Agati Clinical Informatics following Sponsor Authorization of this Statistical Analysis Plan, Database Lock, Sponsor Authorization of Analysis Population and Unblinding of Study Treatment.

For primary and secondary efficacy endpoints, p-value, lower and upper 95% Confidence Limits (CL) will be also presented based on the statistical analysis performed.

The default summary statistics for quantitative variables will be the number of observations (n), mean, standard deviation (SD), median, minimum (min) and maximum (max).

For qualitative variables, the number (n) and percentage (%) of patients with non-missing data per variable of interest will be the default summary presentation, if appropriate and wherever required the number of missing values will be presented as a "Missing" category. If appropriate, 95% confidence intervals around the percentage will be presented.

Time-to-event endpoints will be assessed by the Kaplan-Meier (K-M) method. Time to event curves will be compared (i.e comparisons of each active treatment group versus placebo) using log-rank test and estimates of hazard ratio will be obtained using Cox proportional hazards model after performing diagnostics of proportional hazard assumption (investigated with a time dependent exploratory variable treatment*{log[time to event]}); if the p-value from the Wald Chi-squared statistic for this variable is less than 5% there is evidence of a departure from the adjusted model assumptions.). K-M estimates of median survival time associated with each treatment group will be provided along with 25th and 75th percentiles and their 2-sided 95% CIs (based on Greenwood's method). K-M estimates will be presented at Day 7, 14 and 28 for each treatment group. K-M curves will be plotted comparing treatment groups with the number of patient-at-risk in each treatment group at exact time points. Patients who are ongoing and who are free from event at the time of DB lock will be censored at the DB lock date. Patients who have discontinued without an event will be censored at the date of discontinuation. Patients who are died will be considered as censored with death

date as date of censored.

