6.2.4. Safety monitoring and individual stopping rules

Safety data to be recorded:

- vital signs: blood pressure (systolic and diastolic) and heart rate will be measured daily the patient him/herself using an electronic device. BP and HR measurements will be done with the subject comfortably seated on a chair, with the middle of the cuff on the upper arm at the level of the right atrium (the midpoint of the sternum). Also the body temperature will be measured by 10:00 am using an electronic device.
- SpO₂ will be measured by transdermal oximetry to be collected once daily concomitantly with the BP / HR measurement.
- laboratory tests will be performed on venous blood samples taken from the patient at domicile (drawings performed by a nurse sent to the patient's domicile and delivered to the study site's laboratory). The lab results should be reviewed by the Investigator and clinically relevant changes recorded as AEs. Training to the personell in charge of the samples collection and delivering to the laboratory, and instructions to the laboratory personnel for reporting the lab assessments will be performed at the initial site visit.

Any sign or symptom associated to adverse events will be reported by the patient in an electronic patient diary EXOM GENIUS ROSA and reported during the telemedicine consult. The eDiary should be filled in daily by the patient by 09:00 pm.

All patients will be withdrawn from the study when criteria for supplemental oxygen therapy and/or mechanical ventilation are met. Another stopping rule (patient's withdrawal from study) includes drug related adverse events grade ≥ 3 according to Common Terminology Criteria for Adverse Events (CTCAE) version 5.0 [Common Terminology Criteria for Adverse Events (CTCAE) Last Updated: 03/01/18 available at https://ctep.cancer.gov/protocolDevelopment/electronic_applications/ctc.htm]

Patients are free to withdraw from participation in the study at any time upon request, without any consequence. Patients should be listed as having withdrawn consent only when they no longer wish to participate in the study and no longer authorize the Investigators to make efforts to continue to obtain their outcome data. Every effort should be made to encourage patients to remain in the study for the

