9. STATISTICS

9.1. SAMPLE SIZE

The sample size of the study is calculated based on the following assumptions:

- Virologic assumption: Early treatment with antivirals increases the proportion of patients with undetectable SARS-CoV-2 in upper respiratory tract at day 7 after therapy from 25% to 50%;
- Clinical assumption: Early treatment with antivirals increases the proportion of participants who recover without need of mechanical ventilation and/or supplemental oxygen therapy by the day 14 after therapy from 50% to 75%.

Based on these assumptions and considering a randomization ratio 1:1:1, the sample size will be adaptively determined to achieve a power greater than 80% to show superiority of raloxifene vs placebo in terms of either one primary endpoint (section 7.1.1) and controlling the one-sided alpha below 0.025.

Sample size will be determined through the following steps:

- an interim analysis will take place when 50 participants per arm (N=150) have reached their primary endpoints (i.e. assessments available).
 - In case of efficacy of at least one treatment arm or futility of both arms (see criteria in section 9.3) the study enrolment will be stopped,
 - otherwise the actual number of new participants in each arm may be blindly reassessed according to observed efficacy of the best favourable and promising arm;
- in case of continuation of the study to the final stage, it is expected to randomize on average additional 174 patients, depending on sample size reassessment and possible dropping of an ineffective treatment arm. Expected sample size will be between 250 and 450 randomized participants;
- drop-outs of randomized subjects will not be replaced.

This approach allows either to minimize the number of enrolled participants if the experimental assumptions are too conservative or to have a good power level if they are too optimistic.

Pocock's spending functions and conditional power (CP) will be used to control the type I and II errors, considering that interim analysis will be performed when half of the initial planned patients have been reached the primary endpoints (i.e. assessments available).

Bonferroni method is used to adjust for multiple endpoint vs treatment comparisons.

Sample size calculation has been performed through simulation (100000 replications). The statistical software used for simulation was SAS®, Version 9.4.

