In the SAS® procedure PROC GENMOD, a Type III analysis will be performed by adding the model options: TYPE3, DIST=BIN and LINK=LOGIT. REPEATED statement will be used to consider visit and TYPE=UN option used for correlation-matrix. If the model does not converge then appropriate TYPE would be applied for correlation-matrix.

The following time-to-event endpoints will be analysed according to SAP section 4.4 methods.

- i. Time to reach undetectable SARS-CoV-2 at PCR
- ii. Time to get relieved from supplemental oxygen therapy (NEWS ≤ 2) and/or mechanical ventilation
- iii. Overall survival

Analyses will be performed on FAS population.

3. Proportion of patients in each NEWS category at Day 7, 14 and 28 after randomization will be summarized by frequency and percent by treatment and visit for FAS population.
4. NEWS score at Day 7, 14 and 28 after randomization will also be summarized using descriptive statistics by treatment and visit for FAS population.
5. Proportion of hospitalized patients who at the beginning of the study were at domicile isolation at day 7, 14 and 28 after randomization will be analysed using comparison of proportions (i.e comparisons of each active treatment group versus placebo at each assessment day) through Fisher's exact test and will be summarized using frequency and percent by treatment and visit. Analyses will be performed on FAS population.

6. Proportion of patients admitted to intensive care at Day 7, 14 and 28 after randomization will be analysed using comparison of proportions (i.e comparisons of each active treatment group versus placebo at each assessment day) through Z-test and will be summarized using frequency and percent by treatment and visit. Analyses will be performed on FAS population.
7. Overall survival will be analysed according to time-to-event methods described in SAP section 4.4.
8. Quality of life questionnaire (EQ-5D-5L) at 3 months after the randomization will be summarized using appropriate descriptive statistics by treatment. The number and proportion of subjects of each level (1 - no problems, 2 - slight problems, 3 - moderate problems, 4 - severe problems, 5 - extreme problems) for each dimension (mobility, self-care, usual activities, pain/discomfort, and anxiety/depression) will be reported.
Analyses will be performed on FAS population.

Patient's data will be listed for all secondary endpoints.

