14.1.3 DERIVATION

Pre-menopausal status – Female patients with child-bearing potential will be considered.

Post-menopausal status – Female patients with non-child-bearing potential will be considered.

Status – Male, Female with pre-menopausal status and Female with post-menopausal status will be considered for “Status” variable derivation for the Analysis.

Time to reach undetectable SARS-CoV-2 at PCR:

Patients who have experienced the event (undetectable SARS-CoV-2 at PCR), their date of PCR result confirmation will be used for time duration calculation.

Time to reach undetectable SARS-CoV-2 at PCR = (Date of undetectable SARS-CoV-2 at PCR / Censored date – Treatment Start date) + 1

Time to get relieved from supplemental oxygen therapy (NEWS ≤ 2) and/or mechanical ventilation:

Patients who have experienced the event (relieved from supplemental oxygen therapy (NEWS ≤ 2) and/or mechanical ventilation), their date of confirmation will be used for time duration calculation.

Time to get relieved from supplemental oxygen therapy (NEWS ≤ 2) and/or mechanical ventilation = (Date of relieved from supplemental oxygen therapy (NEWS ≤ 2) and/or mechanical ventilation / Censored date - Treatment Start date) + 1

Overall Survival:

Overall Survival = (Date of Death / Censored date - Treatment Start date) + 1

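### Time to undetectable SARS-CoV-2 is censored at death and at withdrawal for oxygen or ventilation, so its Kaplan-Meier estimates rest on an untested assumption that these patients clear virus at the same rate as the others

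*SAP*

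**What the plan says.** SAP 4.4 sets one rule for all endpoints of this type: "Time-to-event endpoints will be assessed by the Kaplan-Meier (K-M) method", with log-rank and Cox comparisons of each dose against placebo and Kaplan-Meier estimates at days 7, 14 and 28. On censoring it says "Patients who have discontinued without an event will be censored at the date of discontinuation", and for deaths "Patients who are died will be considered as censored with death", the date of death being the censoring date.

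SAP 14.1.2 brings the virologic endpoint under this rule: "The following time-to-event endpoints will be analysed according to SAP section 4.4 methods", and the first item listed is "Time to reach undetectable SARS-CoV-2 at PCR". SAP 14.1.3 measures time from treatment start to "Date of undetectable SARS-CoV-2 at PCR / Censored date" and makes no exception for death or progression.

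Protocol 6.2.4 states: "All patients will be withdrawn from the study when criteria for supplemental oxygen therapy and/or mechanical ventilation are met". Other passages point elsewhere. Protocol 6.3 keeps patients who stop study drug under observation for efficacy and safety, yet also lists documented disease progression as a reason for premature discontinuation. SAP 7.3.2 lists disease progression as a reason for stopping treatment but not for leaving the study.

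The only sensitivity analysis (SAP 8.3) repeats the two binary primary analyses in the per-protocol set. It does not touch the censoring.

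**The concern.** Kaplan-Meier treats a censored patient as having the same future chance of clearing as those still under observation. That cannot hold for a patient who has died. For a patient withdrawn because the disease progressed, clearance may still occur unseen, but there is no reason to take for granted that it occurs at the same rate. If progressors clear more slowly, the curve is too high. The error is larger in the arm with more progression, so a real difference between arms would be shrunk. The protocol synopsis names a shorter duration of viral shedding as an aim of the trial, and these are the analyses that address duration.

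**Working it through.** The documents give no figure for this endpoint, so there is nothing to reproduce first. The size depends on two quantities they do not supply: how many patients are withdrawn for oxygen or ventilation, and how fast those patients clear.

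**Inputs**
- Swabs at days 7, 14 and 28 (Protocol 6.2.2).
- Overall clearance by day 7: 25% placebo, 50% active (Protocol 9.1).
- Progression by day 14, upper case: 50% placebo, 25% active. This is the complement of the planning assumption for the "proportion of participants who recover without need of mechanical ventilation and/or supplemental oxygen therapy by the day 14 after therapy from 50% to 75" per cent.
- Progression, lower case: 20% and 10% (assumed). The 20% matches the 14% severe plus 6% critical disease in Protocol 2.1; the 10% is half of that.
- Progressors clear at r times the hazard of the others throughout (assumed). Hazards are constant, with no withdrawals after day 14.

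**Formulas.** Let w be the proportion withdrawn by day 14, a = exp(−7λ) the probability that a non-progressor has not cleared in 7 days, and b = a^r the same for a progressor.
- Solve (1−w)a + wb = 1 − (day-7 clearance).
- On study at day 7: n = 1−w non-progressors and p = √(1−w) − (1−w) later progressors.
- True clearance at day 14 = 1 − (1−w)a² − wb².
- 1−K-M at day 14 = 1 − a(na + pb)/(n+p).
- Documented clearance, with withdrawn patients counted as not cleared = n(1−a²) + p(1−b).

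**Equal rates (r = 1).** 1−K-M equals the truth: 43.8% placebo and 75.0% active. Documented clearance at 50%/25% progression is 27.1% and 62.1%.

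**Half rate (r = 0.5), placebo, w = 0.5.** 0.5b² + 0.5b = 0.75 gives b = 0.8229, a = 0.6771; n = 0.5, p = 0.2071.
- True: 1 − 0.5×0.4585 − 0.5×0.6771 = 43.2%.
- 1−K-M: 1 − 0.6771×(0.3386+0.1704)/0.7071 = 51.3%.
- Documented: 0.5×0.5415 + 0.2071×0.1771 = 30.7%.

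**Half rate, active, w = 0.25.** b = 0.6667, a = 0.4444; n = 0.75, p = 0.1160.
- True: 1 − 0.75×0.1975 − 0.25×0.4444 = 74.1%.
- 1−K-M: 1 − 0.4444×(0.3333+0.0774)/0.8660 = 78.9%.
- Documented: 0.75×0.8025 + 0.1160×0.3333 = 64.1%.

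The lower case uses the same formulas, with b = 0.8513 (placebo) and 0.6919 (active). Day-14 results for r = 0.5, with errors from unrounded values:

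| Progression | Arm | True | 1−K-M (error) | Documented (error) |
|---|---|---|---|---|
| 50% | placebo | 43.2 | 51.3 (+8.0) | 30.7 (−12.5) |
| 25% | active | 74.1 | 78.9 (+4.8) | 64.1 (−10.0) |
| 20% | placebo | 43.5 | 46.5 (+3.0) | 39.4 (−4.1) |
| 10% | active | 74.6 | 76.6 (+2.0) | 70.9 (−3.7) |

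At 50%/25% the active-minus-placebo difference is 30.9 points in truth, 27.7 by Kaplan-Meier and 33.3 by documented clearance. So one estimator shrinks it and the other inflates it.

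**Timing of the slowing.** If progressors slow only after they progress, the day-14 overstatement falls to 4.9 and 2.9 points.

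**Death alone.** Assume 5% die by day 28 at a constant rate, so 98.73% are alive at day 7 and 97.47% at day 14. Placebo: 0.9873×0.25 + 0.9747×0.75×0.25 = 43.0% against 43.8%. Active: 0.9873×0.50 + 0.9747×0.50×0.50 = 73.7% against 75.0%. Death moves the estimate by about one point, so the mandated withdrawal is the main driver.

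**Precision.** 68/3 is about 23 per arm. At that size the simulated standard error of the day-14 Kaplan-Meier estimate is about 14 points (placebo) and 10 (active) at 50%/25% progression. The Kaplan-Meier errors are then 8.0/14 = 0.6 and 4.8/10 = 0.5 of a standard error. On the same yardstick they are 3.0/14 and 2.0/10, about 0.2, at 20%/10%.

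**The case against.** The strongest reply has four parts.

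1. **Progressors may not leave the study.** Protocol 6.3 and SAP 7.3.2 can be read as keeping them in. Recording ICU admission and survival to day 28, and analysing time to relief from oxygen, presuppose follow-up after oxygen starts. If these patients are swabbed, only deaths and other discontinuations are censored, and the effect is small. This stands as a qualification. It does not remove the point, because Protocol 6.2.4 says the opposite in plain terms and Protocol 6.3 itself lists progression as a reason for discontinuation.

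2. **Withdrawal for oxygen is not a competing event.** It hides clearance but does not prevent it. This stands. A reader might set 43.8% beside 27.1% and infer that Kaplan-Meier overstates placebo clearance by about 17 points. In that equal-rate case Kaplan-Meier is exactly right, and the lower figure is a different quantity: documented clearance without progression. With rates halved, that quantity is further from true clearance than Kaplan-Meier is. Replacing the main estimator with it would be a debatable change of estimand.

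3. **The 50%/25% rates are a stretch.** They are planning rates for a clinical endpoint that SAP 14.1.1 derives from NEWS and ventilation, which is not the trigger in Protocol 6.2.4. This stands, hence the lower case.

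4. **The stakes are limited.** The endpoint is secondary. The primary day-7 endpoint and the day-14 and day-28 proportions are binary and do not use this rule. This also stands.

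**Conclusion.** The point holds in a limited form. The plan censors at death and, on the wording of Protocol 6.2.4, at withdrawal for progression, and it tests neither. Kaplan-Meier is unbiased for clearance if progressors clear at the same rate, apart from about one point for deaths at an assumed 5% by day 28. At half the rate it overstates day-14 clearance by about 8 and 5 points (50%/25% progression) or 3 and 2 points (20%/10%). Counting withdrawn patients as not cleared understates it by about 12.5 and 10, or 4 and 4. Leaving sampling error aside, the two estimates bracket true clearance whenever progressors clear no faster than others.

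The documents do not show that Kaplan-Meier is in fact biased by a given amount, since they give neither the progression rate nor the clearance rate after progression. The sizes rest on those assumptions and on constant hazards. This is a cheap improvement to a secondary analysis and does not threaten the primary result.

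**What to change.** In SAP 4.4 and 14.1.2, before unblinding:

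1. Treat death as a competing event for time to undetectable PCR. Dead patients who had not cleared stay in the denominator as not cleared to day 28.
2. Keep Kaplan-Meier, log-rank and Cox. Add, as a pre-specified sensitivity analysis, the Aalen-Johansen cumulative incidence at days 7, 14 and 28 with withdrawal for oxygen or ventilation as a competing event. Label it documented clearance without progression, and present the two estimates as a range.
3. Reconcile Protocol 6.2.4, Protocol 6.3 and SAP 7.3.2 on whether patients who meet oxygen or ventilation criteria leave the study. Where later swabs were collected, use them instead of censoring.

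The cost is SAP wording and one extra set of estimates, with no new data. The added percentages will be lower than the Kaplan-Meier ones and need their label to avoid misreading. In the half-rate case at 50%/25% progression the range spans about 1.5 standard errors per arm (20.6/14 and 14.8/10), so it will look wide at this sample size.
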